For financial reasons, both for the patient and for society, the government promotes the development of generic drugs at a lower cost and encourages pharmacists to make transition with patients. Many patients using the original Travoprost (Travatan Z) have their treatment modified with generic Travoprost, often without the consent of their treating physician. In Canada, a generic ophthalmic drop with the same active ingredient, at the same concentration as the reference drug, is presumed to be bioequivalent, without the need for a comparative efficacy study. [3]. It is known that Latanoprost, another prostaglandin analogue, may be less stable in generic form than in its original version (Xalatan) under certain conditions. Variations in the concentration of Latanoprost and certain physicochemical properties, such as pH , the material of the container, the size of the drop distributed, are possible which can influence the bioavailability and therefore the effectiveness of the drug [4] [5] [6]. Finally, a variation of the non-medicinal ingredients between the 2 drugs may result in a difference in the type and frequency of the adverse effects, and even affect the efficacy of the product.

In terms of therapeutic efficacy and safety of care, and for reasons of health care costs, it is important to demonstrate whether there is a therapeutic equivalence between generic Travoprost and the brand Travoprost (Travatan Z).

Is this a pilot study? yes no

1a. Review of the literature

Currently, there are many controversies in the literature on the therapeutic equivalence of anti-glaucoma drops and the opinion among experts differ.

Ophthalmic drop may not be as effective as the reference drug, as the efficacy of the generic drug does not need to be proven for market entry in Canada [3].

IOP may be less well controlled with generic Latanoprost, due to variations in the physicochemical properties of the solution, including Latanoprost concentration. These variations are due, among other things, to the properties of the bottle used or the non-medicinal ingredients that differ from the reference medicine [4][5][6][7].

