A 2007 study by Narayanaswamy et al. demonstrated a difference between the generic and original versions of Latanoprost. This pilot study involving 30 patients in a single center in India seemed to demonstrate that generic Latanoprost was less effective than Xalatan in lowering IOP. [8]. However, this is only a small study and some questions about the reliability of the results have surfaced, including concerns regarding the improper storage of the generic Latanoprost used.

On the other hand, several studies have shown an equivalence between the generic drug and the original. A randomized, double-blind study in 2011 by Diguini et al., involving 184 patients, demonstrated the non-inferiority of a generic version of Latanoprost compared to Xalatan.[9]. On the other hand, the generic version used in this study had a composition qualitatively and quantitatively identical to Xalatan, which is often not the case [4][10]. Another randomized multicentre study, by Allaire et al., included 266 patients with diagnosis of primary open angle glaucoma and ocular hypertension. Each patient was assigned to the generic Latanoprost group or the Xalatan group in a ratio of 1: 1. This study demonstrated therapeutic equivalence as well as the same safety profile [11]. Finally, a randomized crossover study by Golan et al. in 2015, compared Glautan, a generic version of Latanoprost, to Xalatan in 19 patients. The hypotensive effect and ocular side effect profile was comparable [12].

2. Objectives

The primary goal was to determine if generic Sandoz-Travoprost is as effective as brand Travatan Z in lowering intraocular pressure, as measured using Goldmann applanation tonometry.

The secondary goal was to determine if patients tolerate generic Sandoz-Travoprost as well as brand Travatan Z, using a questionnaire.

3. Methodology

a. Study Design

Randomized controlled clinical trial, unblinded, crossover trial.

The crossover design was chosen to achieve the power required all the while limiting the number of patients required.

This study was not blinded to reproduce as much as possible the real situation experienced in clinic by the patients and the doctors. The use of masked bottles by the pharmacy was considered. However, some studies have suggested that the different characteristics of drop bottles may have an impact on the size of the drop or the concentration of the drug after 30 days[14]. So it was decided to use the original bottles.

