Cardiovascular: angina pectoris (1% to 5%), bradycardia (1% to 5%), chest pain (1% to 5%), hypertension (1% to 5%), hypotension (1% to 5%)

Central nervous system: Anxiety (1% to 5%), depression (1% to 5%), headache (1% to 5%), pain (1% to 5%)

Dermatological: hyperpigmentation of eyelashes, increased growth of eyelashes

Endocrine and metabolic: hypercholesterolemia (1% to 5%)

Gastrointestinal: dyspepsia (1% to 5%), gastrointestinal disorders (1% to 5%)

Genitourinary: prostate disease (1% to 5%), urinary incontinence (1% to 5%), urinary tract infection (1% to 5%)

Hypersensitivity: Hypersensitivity Reactions (1% to 5%)

Infection: Infection (1% to 5%)

Neuromuscular and skeletal: arthritis (1% to 5%), back pain (1% to 5%)

Respiratory: Bronchitis (1% to 5%), flu-like symptoms (1% to 5%), sinusitis (1% to 5%)

Post-marketing and / or case reports :

Asthma, tachycardia

vi. Contraindications

Allergy to prostaglandin analogues or any of the other ingredients of the product

Being pregnant or considering pregnancy (Risk Factor C for pregnancy)

vii. Interactions

Non-steroidal anti-inflammatory drug: may increase the therapeutic efficacy of prostaglandins

viii. Pharmacodynamics and pharmacokinetics

Start of action: 2 hours

Maximum effect: 12 hours

Half life: 45 minutes

ix. Inactivation and elimination

Inactivation by the kidneys, liver and lungs.

4. Study population

a. Target population:

All adult patients with primary open angle glaucoma, normotensive glaucoma, or ocular hypertension requiring pharmacological treatment seen at CHUS.

5. Sample size and inclusion / exclusion criteria

The calculation of the sample size is based on a paired t test, assuming a normal distribution of intraocular pressure. To demonstrate an equivalence between Travoprost original (Travatan Z) and generic Travoprost, a sample size of 69 patients will be required. This will detect a difference of 1.5mmHg with a power of 80% and an alpha of 0.05, assuming a standard deviation of 3.5mmHg. Assuming a loss at follow-up of 10%, the required number of patients is 76.

a. Inclusion criteria

- To be of age
- Be able to consent and sign the consent form
- Have a diagnosis of primary open angle glaucoma, normotensive glaucoma, or ocular hypertension requiring pharmacological treatment

b. Exclusion criteria

- Angle closure glaucoma
- Having had laser iridotomy
- Allergy known to Travatan or Travaprost, or to any other components of the products

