
Group 4 (Patient already randomized to receive generic Travoprost first)
	
 • Presentation of the study to the patient • Obtaining consent • A bottle of generic Travoprost given with instruction to instill a drop at bedtime in the eye reaches 	
 • IOP taken by the resident • Complete the questionnaire on the comfort of the treatment • A bottle of Travoprost original (Travatan Z) given with instructions to instill a drop at bedtime in the eye reaches 	
 • IOP taken by the resident • Complete the questionnaire on the comfort of the treatment • End of the study

9. Data analysis

The database will be created with Microsoft Excel.

Statistical calculations will be done with SPSS v20.

a. Comparison of the composition of the different groups

A t-test will be used for continuous variables (if the data are not normally distributed, a Mann-Whitney test will be used).

A Chi-square test will be used for categorical variables (if the frequency is less than 5 for a variable, an exact Fisher test will be used).

b. Comparison of groups at the end of the study

A paired t test will be used if the data is normally distributed (otherwise, a Wilcoxon test will be used).

c. Analysis of the therapeutic effect of drugs

An ANOVA test will be used to compare the effect of the treatments over time (an appropriate transformation will be applied to the data if it is not normally distributed).

d. Comparison of adverse effects between the two treatments

A McNeman test will be used to see if each side effect is as common with both treatments.

e. Comparison of compliance with each treatment

A paired t test will be used to see if patients have the same compliance for each treatment (Wilcoxon test if non-normal data).

10. Limitations

There is a potential bias of information if a patient believes that the generic is less effective, which could lead to a decrease in compliance or a change in dosage by the patient (eg: he could put it twice a day and not once). To counter this bias, the importance of abiding by the prescribed posology will be explained to patients.

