To avoid a learning bias, patients who start topical treatment for the first time will be told how to instill the drops during the initial outpatient visit. This instruction will be given by the resident to show the correct way to instill eye drops. A practice will then be performed using a new bottle of artificial tears. For those who are already taking Travoprost (Travatan Z) or generic Travoprost, they will be asked, during their first outpatient visit, to demonstrate how they instill their gout using a new bottle of artificial tears. If necessary, they will receive a short lesson given by the resident.

The loss to follow-up, inevitable in a prospective study, would lead to an information bias. The sample size has therefore been increased by 10%.

11. Ethical considerations

Adverse effects related to the use of Travoprost, as well as the patient's required time and movement, are the only real disadvantages. Follow-up will be provided by the treating team.

12. Anticipated benefits

With the information obtained as to the equal or lesser effectiveness of generic Travoprost compared to the original Travoprost (Travatan Z), we will be able to better inform patients asking if the generic version of their ophthalmic drop is equivalent reference drug. If we find equal efficiency, the savings could be remarkable. However, if we find less efficiency, then we

can ensure that the Travoprost served to our patients is the original Travoprost (Travatan Z) and not a generic, ensuring better control of IOP and therefore better control of the disease.

13. Dissemination of results

We hope to publish the results of this study in a specialized journal in ophthalmology and present them at local, national and international conferences. The results could also be communicated to pharmacists, to raise awareness of the effectiveness (or lack of effectiveness) of generic Travoprost.

14. Schedule

2015/08 Submission to the Scientific and Ethics Committees

2016/07 Start of patient recruitment

2017/07 Data analysis

2017/10 Writing and publication of the article

15. Budget

The cost of the study will be solely due to the ophthalmic drops delivered to patients.

Sample size:	69
Loss to follow-up:	10%
Increased sample size to compensate for anticipated loss to follow-up:	76
Cost per bottle of generic Travoprost (5mL):	\$44.99
Cost of generic Travoprost with taxes	\$51.74
Bottles of generic Travoprost per patient	1
Total per patient (including taxes):	\$51.74

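### The stated aim is equivalence, but the planned IOP analyses only test for a difference, with no equivalence margin, confidence-interval criterion or decision rule

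*Combined protocol and SAP*

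**What the plan says.** The aim appears in four places.

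- The background text before section 1a: "it is important to demonstrate whether there is a therapeutic equivalence between generic Travoprost and the brand Travoprost (Travatan Z").
- Section 2 (Objectives): "The primary goal was to determine if generic Sandoz-Travoprost is as effective as brand Travatan Z in lowering intraocular pressure".
- Section 5 (Sample size): "To demonstrate an equivalence between Travoprost original (Travatan Z) and generic Travoprost, a sample size of 69 patients will be required". The next sentence reads: "This will detect a difference of 1.5mmHg with a power of 80% and an alpha of 0.05, assuming a standard deviation of 3.5mmHg".
- Section 12 (Anticipated benefits) expects a verdict of equal or lesser efficacy and plans action on either: "If we find equal efficiency, the savings could be remarkable".

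The analysis is in section 9. Section 9a compares group composition, 9d adverse effects and 9e compliance. That leaves 9b, "A paired t test will be used if the data is normally distributed (otherwise, a Wilcoxon test will be used"), and 9c, "An ANOVA test will be used to compare the effect of the treatments over time". Neither names IOP, but no other part of section 9 can carry the primary IOP comparison.

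The text supplied contains no equivalence or non-inferiority margin, no confidence interval for the IOP difference, no TOST procedure and no criterion for calling the products equal.

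**The concern.** A paired t test, a Wilcoxon test and an ANOVA can each give evidence that two treatments differ. None can give evidence that they do not. Failing to reject the null is compatible with a difference larger than the 1.5 mmHg that section 5 treats as worth detecting, and it becomes more likely as data become fewer or noisier. A badly run or under-recruited trial would therefore find it easier to look equal.

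The plan does not say that p > 0.05 will be read as equality. That is an inference: it is the only route to such a conclusion that the named tests leave open.

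This is the primary objective. Section 12 intends the result to inform patients and to settle whether the brand should be the product served, and section 13 intends it to reach pharmacists. A margin chosen after the data are seen would carry little weight.

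**Working it through.** **Inputs from section 5.** Difference 1.5 mmHg, SD 3.5 mmHg, power 80%, alpha 0.05, paired t test, 69 evaluable patients. The plan does not say whether alpha is one- or two-sided, or whether 3.5 is the SD of a single measurement or of the within-patient difference.

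**Reproducing 69.** Power comes from the noncentral t distribution with n − 1 degrees of freedom and noncentrality 1.5·√n / SD_diff.

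- Two-sided, SD_diff = 3.5: 45 pairs.
- Two-sided, SD_diff = 3.5 × √2 = 4.95 (uncorrelated measurements): 88 pairs.
- One-sided 0.05, SD_diff = 4.95: 69 pairs, an exact match.
- Two-sided, SD_diff = 4.38: 69 pairs. This SD is back-solved and implies a within-patient correlation of about 0.22, which the plan does not state.

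The figure can thus be reproduced, but only as the size of a difference test. The three SDs (3.5, 4.38 and 4.95) are carried forward as assumptions.

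**Difference test with 69 pairs.** SE = SD_diff / √69, t(0.975, 68) = 1.995, t(0.95, 68) = 1.668. The largest non-significant observed difference is 1.995 × SE. Its upper 90% confidence limit is (1.995 + 1.668) × SE.

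| SD_diff (assumed) | 3.5 | 4.38 | 4.95 |
|---|---|---|---|
| SE (mmHg) | 0.421 | 0.527 | 0.596 |
| P(two-sided p > 0.05), true difference 1.5 | 6% | 20% | 30% |
| P(two-sided p > 0.05), true difference 1.0 | 35% | 54% | 62% |
| Largest non-significant difference (mmHg) | 0.84 | 1.05 | 1.19 |
| Upper 90% limit at that difference (mmHg) | 1.54 | 1.93 | 2.18 |

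Under the one-sided reading that reproduces 69 at SD 4.95, the first probability is 20% rather than 30%. With only 20 pairs, the two-sided test misses a true 1.5 mmHg difference 56% to 75% of the time across the three SDs, so losing data favours a finding of no difference.

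**Equivalence test.** TOST concludes equivalence when |observed difference| + t(1 − α, n − 1) × s/√n < margin, where s is the sample SD of the differences. Power was obtained by integrating over the chi-square distribution of the sample variance. The margin is taken as 1.5 mmHg, an assumption because the plan does not call it a margin.

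| SD_diff (assumed) | 3.5 | 4.38 | 4.95 |
|---|---|---|---|
| P(conclude equivalence), true difference 1.5, 5% per side | 5% | 5% | 5% |
| Power with 69 pairs, true difference 0, 5% per side | 94% | 76% | 60% |
| Power with 69 pairs, true difference 0.5, 5% per side | 76% | 57% | 46% |
| Power with 69 pairs, true difference 0, 2.5% per side | 88% | 60% | 40% |
| Pairs for 80% power, true difference 0, 5% per side | 49 | 75 | 95 |
| Pairs for 80% power, true difference 0.5, 5% per side | 78 | 121 | 154 |
| Pairs for 80% power, true difference 0, 2.5% per side | 60 | 92 | 117 |

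**One-sided non-inferiority.** With a 1.5 mmHg margin and a true difference of 0, power equals that of a one-sided test to detect 1.5 mmHg. With 69 pairs at one-sided 5% this is 97% at SD 3.5, 88% at 4.38 and 80% at 4.95.

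**The case against.** The strongest defence is that 1.5 mmHg is an implicit margin, because section 5 mentions equivalence and the 1.5 mmHg in consecutive sentences. A reader can see an intended threshold there. But the figure is defined as a difference to detect, is not justified as a margin and does not reappear in section 9, so nothing links it to a conclusion.

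Second, if 3.5 mmHg is the SD of the paired differences, the two approaches nearly coincide with 69 pairs: the error at a true 1.5 mmHg is 6% against 5%, the confidence limit overshoots 1.5 by only 0.04 mmHg, and TOST power is 94%. This stands, and the larger figures depend on SDs the plan does not give. However, a two-sided paired t test with SD 3.5 needs 45 pairs, so this reading does not reproduce the plan's own 69. Any closeness would also be an accident of sample size and SD; no rule in the plan secures it.

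Third, the aim is not worded uniformly. Section 2 asks whether the generic is as effective, and section 12 speaks of "With the information obtained as to the equal or lesser effectiveness of generic Travoprost". Both fit a one-sided non-inferiority question at least as well as two-sided equivalence. This also stands, and it shapes the remedy. It does not rescue the plan, because non-inferiority needs a margin and a rule too.

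**Conclusion.** The concern holds and needs correcting before analysis. As written, section 9 cannot support the conclusion of equal efficacy that the trial is designed to reach. This finding does not depend on 69 being the wrong number.

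Its practical size does depend on the undefined SD. If non-significance were read as equality, a true 1.5 mmHg difference would pass as equal in 6% to 30% of trials with 69 pairs, and in 20% at the plan's own nominal 80% power. Whether 69 pairs suffice for an equivalence claim is open for the same reason: they do if 3.5 mmHg is the SD of differences and the true difference is near zero, and they fall short of 80% power at 4.38 or 4.95. The equivalence figures assume a symmetric 1.5 mmHg margin, normally distributed differences and, unless stated, a 90% confidence interval.

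**What to change.** In sections 9b and 9c, identify the primary IOP analysis and state: *Equivalence is concluded only if the two-sided 90% confidence interval (TOST, 5% per side) for the mean within-patient IOP difference, generic minus brand, lies wholly within the pre-specified margin.* In addition:

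- The sponsor should state and justify the margin. The 1.5 mmHg in section 5 is the obvious candidate.
- If the Wilcoxon branch is used, apply the same rule to a 90% Hodges-Lehmann interval.
- State that p > 0.05 will not be reported as equivalence.
- If only lesser efficacy is to be excluded, say so in section 2 and define a one-sided non-inferiority rule with its own margin.
- In section 5, say whether 3.5 mmHg is the SD of within-patient differences, and restate the power of 69 pairs under the chosen rule.

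The analysis change is wording only and uses the same data. The real cost is power. If the SD of differences is 4.95 mmHg, 80% equivalence power at a true difference of zero needs 95 evaluable pairs, or 95 / 0.90 = 106 recruited. At the budgeted $51.74 per patient for generic drug that is 106 × 51.74 = $5,484, against an award of $4,000. The current plan leaves 4,000 − 3,926.95 = $73.05, enough for about one more patient. The sponsor may therefore have to find funds, accept lower power, or accept an inconclusive result where a difference test would have been read as equal.

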- Use of other hypotensive ophthalmic drops (except for Travatan Z or generic Travoprost)
- Use of corticosteroid
- To be pregnant
- Breast-feed
- Being monocular
- Have had glaucoma surgery such as trabeculectomy and Tube implants (eg Baerveldt, Ahmed). Patients who have had selective laser trabeculoplasty will also be excluded.
- Active intraocular inflammation
- Ocular surface disease that may interfere with an accurate measurement of IOP
- Any clinically significant eye disease that may interfere with the study

6. Recruitment

The subjects will be adult patients seen in the outpatient ophthalmology clinic of the Hotel-Dieu de Sherbrooke, who require or already use a pharmacological treatment of Travoprost original (Travatan Z) or generic Travoprost and meeting the eligibility criteria.

The subjects will be recruited at the outpatient ophthalmology clinic of the Hôtel-Dieu de Sherbrooke after a new consultation or a follow-up appointment. The physician resident will present the study to the patient, complete the consent form and obtain their signature.

The randomization will be done beforehand.

The only inconveniences for patients, no matter what group they are in, are the 2 follow-up visits, one to 3 weeks and one to 6 weeks.

7. Variables and data collection

Variable	Type	Method of measurement
age	continuous	From the chart
sex	dichotomous	From the chart

ethnic group	categorical	From the chart
diagnostic	categorical	From the chart
IOP	continuous	Goldmann applanation tonometry
initial treatment	dichotomous	From the chart
MD (visual fields)	continuous	Visual field; at the initial appointment
side effects	dichotomous	questionnaire; at the 3 week and 6 week appointments
treatment adherence (number of days missed)	continuous	questionnaire; at the 3 week and 6 week appointments

The data will be collected by the resident in charge of the project, who will be responsible for their management. Registration will be in accordance with the accepted standards of confidentiality as described in the Act respecting health services and social services.

We will use the Goldmann tonometer, a device on the slit lamp, to measure intraocular pressure. Currently, she is the gold standard for measuring intraocular pressure[13].

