The questionnaire given to patients will be a home-based questionnaire designed to check whether patients have had difficulty putting the drops, if they forget to put them on and if they have had adverse effects. The questionnaire will contain a list of side effects that patients can easily identify. The questionnaire will be filled verbally with the patient, and not just read and checked.

The mean deflection index (MD), a parameter given by the automated visual field, is an accepted measure in the literature for stratifying the glaucoma stage, either mild, moderate, or advanced [13].

8. Study Protocol

a. For patients who are new consultations:

At the first visit, the patient's sociodemographic data will be collected and a complete ophthalmic examination will be performed. This examination will include visual acuity, external examination, evaluation of the cornea, anterior chamber, iris, lens, vitreous, retina and optic nerve (with pharmacological dilatation). Intraocular pressure, gonioscopy, pachymetry and visual field Humphrey SITA fast 24-2. If the patient qualifies for the study, resident [name] will present the study. If the patient agrees, resident [name] will complete the consent form with the patient and get his signature. The patient will receive a bottle of original Travoprost (Travatan Z) or generic Travoprost according to the prior randomization. The patient will receive explanations on how to apply the drops.

During the second visit, at 3 weeks +/- 3 days, the IOP will be taken by resident [name] at 9:00 +/- 1h. A bottle of the other medicine will be given to him.

At the third visit at 6 weeks +/- 3 days, the IOP will be taken by resident [name] at 9:00 +/- 1h. The patient will have completed the study and a prescription from Travoprost will be given.

A questionnaire on tolerance and comfort of drops will be completed with the patient at the second and third visit.

b. For patients who were already followed and treated with brand Travoprost (Travatan Z) or generic Travoprost:

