Group 1 (new randomized consultation to receive Travatan Z first)	
 • Presentation of the study to the patient • Obtaining consent • Taking of IOP • A bottle of Travoprost original (Travatan Z) given with instructions to instill a drop at bedtime in the eye reaches 	
 • IOP taken by the resident • Complete the questionnaire on the comfort of the treatment • A bottle of generic Travoprost given with instruction to instill a drop at bedtime in the eye reaches 	
 • IOP taken by the resident • Complete the questionnaire on the comfort of the treatment • End of the study
Group 2 (New Randomized Consultation to Receive Generic Travoprost First)	
 • Presentation of the study to the patient • Obtaining consent • A bottle of generic Travoprost given with instruction to instill a drop at bedtime in the eye reaches 	
 • IOP taken by the resident • Complete the questionnaire on the comfort of the treatment • A bottle of Travoprost original (Travatan Z) given with instructions to instill a drop at bedtime in the eye reaches 	
 • IOP taken by the resident • Complete the questionnaire on the comfort of the treatment • End of the study

Group 3 (Patient already randomized to receive Travatan Z first)
	
 • Presentation of the study to the patient • Obtaining consent • A bottle of Travoprost original (Travatan Z) given with instructions to instill a drop at bedtime in the eye reaches 	
 • IOP taken by the resident • Complete the questionnaire on the comfort of the treatment • A bottle of generic Travoprost given with instruction to instill a drop at bedtime in the eye reaches 	
 • IOP taken by the resident • Complete the questionnaire on the comfort of the treatment • End of the study

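### The crossover's efficacy tests (9b, 9c) state no period term and neither is named primary; a pre-specified period-adjusted primary analysis would be a cheap improvement.

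*Combined protocol and SAP*

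**What the plan says.** Section 3a describes the design as "Randomized controlled clinical trial, unblinded, crossover trial". Section 8 and its visit table set out two treatment orders, with IOP read at 3 and 6 weeks. The orders are applied to two kinds of patient: 8a is headed "For patients who are new consultations" and 8b "For patients who were already followed and treated with brand Travoprost (Travatan Z) or generic Travoprost". I call these two kinds strata, but the documents do not say that randomisation was stratified by them. On allocation, section 6 says only "The randomization will be done beforehand".

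Two parts of section 9 can bear on efficacy. Section 9b says "A paired t test will be used if the data is normally distributed", with Wilcoxon as the fallback. It does not name its outcome. I read it as IOP, because adverse effects and compliance have their own tests in 9d and 9e. Section 9c says "An ANOVA test will be used to compare the effect of the treatments over time", with a transformation if the data are not normal. Neither mentions period, sequence or stratum, and neither is labelled primary. The only pointer is in section 5: "The calculation of the sample size is based on a paired t test, assuming a normal distribution of intraocular pressure".

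**The concern.** In a two-period crossover, each patient's generic-minus-brand difference contains the treatment effect plus or minus any change in IOP between the two periods. The sign depends on which product came first. A plain paired test averages these differences without regard to order. Any period change therefore cancels only as far as the two sequences are equal in size, and whatever its size it inflates the standard error. A period term removes a change common to all patients.

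The second issue does not depend on a period change. One IOP question has three candidate tests (paired t, Wilcoxon, ANOVA), and the choice between the first two turns on a normality check. With no primary named, the choice can be made after the data are seen.

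**Working it through.** **Inputs from section 5:** target difference 1.5 mmHg, alpha 0.05, power 80%, SD 3.5 mmHg, N = 69 evaluable. The section does not say whether alpha is one- or two-sided, or whether 3.5 is the SD of one IOP or of the within-patient difference.

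**Reproducing 69.** Noncentral-t power for a paired test gives exactly 69 (power 0.802) with one-sided alpha 0.05 and SD_diff = 3.5 × √2 = 4.95, that is, correlation 0. Two-sided, SD_diff 3.5 needs 45 patients and 4.95 needs 88. The two-sided SD_diff that gives 80% at N = 69 is 4.38. This value is back-solved; if 3.5 is the SD of one IOP, it implies correlation 1 − 4.384²/(2 × 3.5²) = 0.22. I use 4.38 as the middle case and 3.5 and 4.95 as the range, all two-sided.

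**Assumptions not in the documents:** IOP shift π from week 3 to week 6 of 0, 1 or 2 mmHg; 35 of the 69 patients new; simple randomisation where stated.

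**Bias of the paired mean.** With treatment effect δ, the expected difference is δ + π (brand first) or δ − π (generic first). The mean is therefore δ + π(n1 − n2)/N.
- 35:34: 1/69 = 0.014 mmHg per 1 mmHg of shift.
- 40:29: 11/69 = 0.159 mmHg per 1 mmHg.
- Under simple randomisation, P(|n1 − n2| ≥ 11) = 0.23 from Binomial(69, 0.5).

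Averaged over randomisation the bias is zero, and simulated 95% CI coverage of the paired t test under simple randomisation is 94.8–95.2%.

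**With a period term.** The estimate is the average of the two sequence means: ½[(δ + π) + (δ − π)] = δ. A shift common to all patients drops out.

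**Shift only in new patients.** Take 40:29 with 23 and 12 new patients.
- Paired: (23 − 12)/69 = 0.159 per 1 mmHg.
- Period term alone: (23/40 − 12/29)/2 = (0.575 − 0.414)/2 = 0.081.
- Period × stratum: 0.

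**Noise.** With near-balanced sequences, the SD entering the paired t test is about √(SD_diff² + π²). At SD_diff 4.38, the 95% half-width is 1.995 × SD/√69. This gives 1.05 mmHg with no shift, 1.08 at 1 mmHg (SD 4.49) and 1.16 at 2 mmHg (SD 4.82). With the period term it stays at about 1.05 for any common shift.

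**Power at 1.5 mmHg (%), used here as a measure of precision.** The paired column averages over simple randomisation (40,000 simulated trials per cell, shift in all patients). The other two are exact for the stated split under any common shift, with variance SD_diff²/4 × (1/n1 + 1/n2) and 67 df.

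| SD_diff | Paired t, shift 0 / 1 / 2 | Period term, 35:34 | Period term, 40:29 |
|---|---|---|---|
| 3.5 | 94.1 / 92.2 / 86.4 | 93.9 | 93.4 |
| 4.38 | 80.2 / 77.8 / 72.0 | 80.0 | 79.0 |
| 4.95 | 70.3 / 68.6 / 63.4 | 69.9 | 68.8 |

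**Cost with no shift.**
- Period term at 35:34: under 0.1 point.
- Period term at 40:29: the variance rises by 1/(1 − (11/69)²) = 1.026, which costs about 0.6 to 1.1 points.
- Period term at 42:27: about 2 points (69.9 to 67.8% at SD_diff 4.95).
- Period × stratum: 0.6–1.5 points on average over simple randomisation; about 1.2–2.3 at 40:29 with 23 and 12 new; 1.8–3.5 in very uneven cells (22/12 new, 13/22 treated).

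**Bias and noise together.** Root-mean-square error at SD_diff 4.38 and a 1 mmHg shift, for paired / period / period × stratum, is 0.541 / 0.531 / 0.535 if all shift and 0.534 / 0.535 / 0.535 if only new patients shift.

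**The case against.** The strongest reply is that the harm is hypothetical. No document shows a period shift, and the plan limits one. Both readings are on treatment, clock time is held to ±1 hour (8a, 8b), and instillation is taught before the first period (section 10). Section 3b puts maximum effect at 12 hours after a dose. That does not exclude later drift, but it gives no support for new patients still changing at week 3. At 1 mmHg the total error barely changes, and a clear gain needs about 2 mmHg, more than the 1.5 mmHg the trial is sized on. All of this stands, and it keeps the point at the level of an improvement.

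The allocation method also matters. Silence in section 6 is not evidence of simple randomisation, and the four groups in the visit table are compatible with separate lists. Blocked within stratum, the bias is at most 0.014 mmHg per 1 mmHg. Only the extra width of the paired interval would then remain, and it matters mainly at the larger shift. The ANOVA in 9c may also be meant to include visit, in which case part of the fix is simply to write 9c out.

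A reader might infer that the paired t test is biased or invalid here. It is not: it is unbiased over randomisation and its coverage is nominal. A reader might also infer that period × stratum must be in the primary model. The documents do not support that either. A shift confined to new patients is only a possibility, and the extra term has a real cost when cells are uneven.

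None of this answers the absence of a named primary analysis.

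**Conclusion.** The point holds as a cheap improvement to the specification. The plan names no primary efficacy analysis and states no period term for a two-period crossover. A period shift would move the estimate by 0.159 mmHg per 1 mmHg at 40:29. At SD_diff 4.38, a 2 mmHg shift in all patients would lower the paired test's power from about 80% to 72%, whereas a period term would hold it at 79–80% for splits between 35:34 and 40:29. At 1 mmHg the gain is small. If sequences are blocked within stratum, there is almost no bias to remove.

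These sizes rest on an assumed shift, an assumed SD of the difference and, for the 23% chance and the averaged power, simple randomisation. The case for naming one primary analysis rests on none of them. The point does not cover carryover, which a period term does not address, or the equivalence decision rule, which is a separate matter.

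**What to change.** 1. In section 9, name one primary analysis: the period-adjusted crossover comparison of week-3 and week-6 IOP. In patients with both readings, regress the generic-minus-brand difference on sequence, coded +1 (brand first) and −1 (generic first), and report the intercept with its CI. This equals a model with treatment, period and a fixed patient effect. Do not centre the sequence code on its sample mean, because the intercept then returns to the plain paired mean (0.159 instead of 0 at 40:29).
2. Do not switch the primary method on a normality test. Keep the plain paired t test, Wilcoxon and 9c as supportive, and list 9c's factors.
3. Pre-specify period × stratum (new versus already treated) as a sensitivity analysis, because a period term alone leaves part of the bias if only new patients shift.
4. State in section 6 how the list was generated, and whether it was blocked and stratified by patient type.

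The change is wording only, with no new patients, visits or data. The primary analysis loses one degree of freedom, plus the small power cost shown in the working when sequences are uneven.
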